### **11.2.4. Pregnancy Test (Urine or Serum)**

Females of childbearing potential will be evaluated for pregnancy at Screening and at the Day 14 or early termination visit (if the early termination visit occurs prior to Day 14) assessment using a urine pregnancy test performed locally unless they are already pregnant. If local regulatory guidelines require a serum pregnancy test, then this modality should be completed in addition to the urine test to complete the pregnancy test.

### **11.3. Vital Signs**

Vital sign measurements (blood pressure, heart rate, respiration rate) will be recorded once at Screening and once at each study visit on Days 3, 7, 14 and/or early termination visit.

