## **7. INVESTIGATIONAL PLAN**

### **7.1. Endpoints**

#### **7.1.1. Primary Endpoint**

The primary endpoint of this study will be safety and include the assessment of AEs, laboratory abnormalities (clinical chemistry, hematology and urinalysis), vital signs and physical examinations.

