**Table 1. BCX1812-306: Schedule of Assessments**

Assessments	Screening 	Baseline  (Pre-dose)	Day 1 Treatment Day 	Day 3	Day 7 (+ 2 days)	Day 14 (+ 3 days) / End of Study	Early Withdrawal
Informed Consent	X						
Inclusion/Exclusion Criteria	X						
Medical History/Physical Exam	X			X 	X 		
Vital Signs 	X			X	X	X	X
Body Temperature 	X	X	X	X	X	X	X
Clinical Chemistries and Hematology 		X			X		X
Urinalysis 		X			X		X
Pregnancy Test (Urine or Serum)	X					X	X
Assessment of influenza symptoms 	X		X	X	X	X	X
Ability to Perform Usual Daily Activities 		X		X	X	X	X
Influenza Related Complications (IRC) 	X			X 	X	X	X
Concomitant Medications Review	X		X	X	X	X	X
Subject Diary Review			X	X	X	X	X
Pharmacokinetic (PK) Sampling			X				
Serum sample for influenza antibody analysis 		X		X	X		X
Swabs for Virology Analysis		X		X	X		X
Rapid antigen test (RAT) or FDA- approved PCR test for influenza A and B on nasal specimen	X						

Assessments	Screening	Baseline (Pre-dose)	Day 1 Treatment Day	Day 3	Day 7 (+ 2 days)	Day 14 (+ 3 days) / End of Study	Early Withdrawal
Study Drug Administration			X				
Adverse Events 	X	X	X	X	X	X	X

- 1 It is expected that the date of Screening, Baseline, and Day 1 (date of study drug administration) will be the same. Day 1 consists of pre and post-dose assessments.
- 2 Vital sign measures will include blood pressure, pulse rate, and respiration rate. Vital signs will be recorded once during Screening, and vital signs will be taken once on remaining study visit days.
- 3 The investigator will record oral body temperature at Screening. Thereafter, the subject or care giver will record oral body temperature approximately every 12 hours in the Subject Diary until temperature normalizes for 48 hours (i.e. temperature without antipyretic is < 37.4°C/ 99.4°F orally for 4 measurements).
- 4 Clinical laboratory assessments performed at Screening are for the purpose of establishing a baseline. Subjects may be enrolled and begin treatment with study drug prior to receiving results. These labs may be done at any visit if necessary for patient management or adverse event monitoring purposes.

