#### 10.1.1. Screening Period

The Screening Period begins at the time of consent of the study subject. The Investigator will conduct the following assessments:

- Review of inclusion and exclusion criteria
- Review and record medical history and concomitant medications
- Conduct an assessment for IRC; if an IRC is suspected, then the physical examination will confirm the actual presence/absence of the IRC. If an IRC is present, the subject meets exclusion criteria 6 and is ineligible for the study.
- Measure oral body temperature
- Conduct a RAT or Food and Drug Administration (FDA)-approved PCR test for influenza A and B on an adequate nasal specimen, in accordance with the manufacturer's instructions. The subject must have a positive RAT result and/or a Food and Drug Administration (FDA) approved PCR test and at least one clinical sign or symptom consistent with influenza (see 2b below).

**OR** have clinical signs and symptoms consistent with acute influenza infection consisting of an oral temperature  $\geq 100^{\circ}\text{F}$  ( $37.8^{\circ}\text{C}$ ) with at least one respiratory symptom of at least moderate severity (cough or rhinitis) and at least one constitutional symptom of at least moderate severity (myalgia [aches and pains], headache, feverishness, or fatigue) (See Section 8.1). **Note: Enrollment at each site by clinical symptoms alone will be approved by the Sponsor at the beginning of each influenza season once influenza has been confirmed in the local community. The Sponsor may withdraw approval for symptomatic screening in any season based upon trends in influenza surveillance data. Prior to Sponsor approval or after approval is withdrawn, Criteria 2 must be met by a positive influenza RAT test and/or PCR. During the period of approval, clinical symptoms alone will be adequate to meet Criteria 2.**

The subject must have at least 1 respiratory symptom (cough, sore throat or nasal symptoms) of at least moderate severity, in addition to at least 1 constitutional symptom (myalgia, headache, feverishness, or fatigue) of at least moderate severity to be eligible for the study

- Measure vital signs (blood pressure, pulse rate, and respiration rate)
- Perform a complete physical examination. Examination of the breast and urogenital system may be omitted as per the institution's/Investigator's clinical routine.

- Perform a urine or serum pregnancy test (non-pregnant females of childbearing potential only)

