##### **10.1.2.2. Day 1/Post-dose**

The following procedures/evaluations will be performed post-dose on Day 1:

- Collect up to 3 plasma samples, where possible, during the following time periods, beginning from the end of dosing until release from the site. For each plasma sample the calendar date and 24-hour clock time of sample collection will be recorded:
  - One time point immediately following completion of the infusion
  - One time point from 30 minutes to 1 hour post-infusion
  - One time point from 1 hour to 3 hours post-infusion
- Train the subject/caregiver on the recording of the following in the subject diary:
  - Subject's body temperature, obtained at approximately 12-hour intervals each day until the temperature normalizes for 48 hours (and 4 hours from last antipyretic medication administration or immediately prior to administration).

- Instruct the subject to assess his/her time lost from work, if applicable, and the recording of the subject's ability to perform usual daily activities using a 0 to 10 visual analogue scale.
- Assessment of signs and symptoms of influenza twice daily beginning on Day 1 (see Section [10.2.2](#)).
- Review and record concomitant medications
- Obtain and record body temperature
- Review and record AEs

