5.3.4. Other Safety Analyses

Exposure to study drug, including infusion time treatment status, will be summarized by age group

and overall.

Descriptive summaries of vital signs measured by study site personnel will be presented by study visit for each age group and overall.

All physical examination findings will be listed by age group and study visit.

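### Vital signs are scheduled before dosing and then not until Day 3, so the scheduled vital-sign data cannot show an acute infusion-related change

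*Protocol*

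**What the plan says.** Protocol 7.1.1 makes safety the primary endpoint and lists as its parts adverse events (AEs), "laboratory abnormalities (clinical chemistry, hematology and urinalysis), vital signs and physical examinations". Footnote 2 of protocol Table 1 gives the content: "Vital sign measures will include blood pressure, pulse rate, and respiration rate". Body temperature has its own row and is not part of that set.

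On timing, Protocol 11.3 says that these measurements "will be recorded once at Screening and once at each study visit on Days 3, 7, 14 and/or early termination visit". In Table 1, and in its copy in SAP 1.2, the vital-sign row is marked at Screening, Days 3, 7 and 14, and Early Withdrawal; the Baseline and Day 1 cells are blank. The footnote adds: "Vital signs will be recorded once during Screening, and vital signs will be taken once on remaining study visit days". Footnote 1 says: "It is expected that the date of Screening, Baseline, and Day 1 (date of study drug administration) will be the same".

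The infusion lasts 15 to 30 minutes (Protocol 9.3). Up to three blood samples for pharmacokinetics (PK) follow where possible, the last described as "One time point from 1 hour to 3 hours post-infusion" (Protocol 10.1.2.2).

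For analysis, SAP 5.3.4 says: "Descriptive summaries of vital signs measured by study site personnel will be presented by study visit for each age group and overall". The output is Table 14.3.6.

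**The concern.** Any effect of an intravenous drug on blood pressure, pulse or respiration during or soon after infusion would be looked for in the first minutes to hours. The plan takes no scheduled reading then, although staff are already drawing blood and recording temperature. The population makes this more than a formality. At least 80 of about 120 subjects are to be 65 or older, and the risk factors in Protocol 8.1 include myocardial infarction, treated angina, treated congestive heart failure, arrhythmia and dialysis. Protocol 5.4 gives more safety data in at-risk groups as a reason for the study.

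At stake is how Table 14.3.6 will be read. A table with no marked change at Days 3, 7 and 14 could be taken as evidence that the infusion has no haemodynamic effect, when it contains no scheduled observation from the relevant period.

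**Working it through.** The plan gives no figure to reproduce. The check compares the scheduling passages, derives one interval and makes one count.

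**1. Scheduling passages side by side**
- Protocol 10.1.1 (Screening): vital signs listed.
- Protocol 10.1.2.1 (Baseline, pre-dose, and dosing): swab, temperature, blood and urine, drug administration, temperature. No vital signs.
- Protocol 10.1.2.2 (Day 1 post-dose): PK samples, diary training, symptom assessment, medications, temperature, AEs. No vital signs.
- Protocol 10.1.2.3 (Day 3): vital signs listed.
- Protocol 11.3, protocol Table 1 and SAP 1.2: Screening, then Day 3 onward.

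These agree. Footnote 2 could be stretched to cover Day 1 when Screening falls on an earlier date. But the Day 1 cell is blank, 11.3 omits Day 1, the two dates are expected to coincide, and the footnote does not say post-dose.

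**2. Interval from dosing to the next scheduled set**
- SAP 3.3.8 counts the date of Day 1 as study day 1, so Day 3 is 3 − 1 = 2 calendar days later: nominally 2 × 24 = 48 hours after the start of dosing.
- From the end of infusion: 48 − 0.5 = 47.5 hours to 48 − 0.25 = 47.75 hours.
- Day 3 has no stated window or clock time. The calendar rule alone allows more than 24 and less than 72 hours. If dosing and visit both fall between 08:00 and 18:00 (my assumption), the range is 48 ± 10, or 38 to 58 hours.

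**3. Count**
Scheduled sets after the infusion on Day 1: 0.

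**4. What the Day 3 change can show**
Change from Screening to Day 3 = change due to recovery + any drug effect still present at about 48 hours. A transient effect that has resolved by then adds nothing. A persisting effect cannot be separated from recovery without a comparator arm. The documents do not say how large the recovery term is.

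**5. What the AE route can show**
The protocol's DAIDS table has no Grade 1 hypotension. Grades 2 and 3 require symptoms, and Grade 4 is shock. Hypertension Grades 1 to 3 rest on measured values. A symptom-free change of either kind is recorded only if somebody takes a reading.

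**6. Size of the remedy**
2 time points × 120 subjects = 240 sets at most, of which at least 2 × 80 = 160 would be in elderly subjects if all were still on site. At three measures per set (blood pressure counted once), 240 × 3 = 720 measures. Because PK samples are drawn only where possible, these are ceilings if every subject attends both draws.

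**The case against.** The documents are consistent, so this is a design choice and not an error. The choice has a context. The drug is approved and given at labelled dosage (Protocol 5.3, 9.1). Safety had been evaluated in 1453 adults, with AE rates similar to placebo and oseltamivir (Protocol 5.3.1.2). A thorough QT study at 600 and 1200 mg was negative (Protocol 5.3). No passage reports an acute haemodynamic signal. AEs are reviewed after dosing on Day 1, and the AE definition (Protocol 11.1.1.1) covers unintended signs as well as symptoms, so an abnormal reading found in ordinary care could be recorded. Added readings would also lack a control arm and could be affected by antipyretics or infused fluid.

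Much of this stands, and it limits the point. It does not close the gap. The prior data described are pooled AE rates and, in healthy adults, repolarisation; they are not peri-infusion vital signs in elderly or cardiac subjects. AE review cannot pick up a silent change that nobody measures. A within-subject comparison over about an hour is imperfect, but much less exposed to recovery than one over two days.

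A reader might infer that vital signs are not measured at all until 48 hours, or that the primary endpoint cannot detect an acute effect. Neither is supported. A pre-dose set is taken at Screening, and AEs, unscheduled readings or an early withdrawal visit may capture some events. Nor do the documents show that most subjects are febrile at Screening: the test-positive route in Protocol 8.1 needs only one sign or symptom.

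**Conclusion.** The point holds for the scheduled vital-sign data. There is one pre-dose set, none on Day 1 after the infusion, and the next is nominally 48 hours after dosing (38 to 58 hours under the clock-time assumption above). Those data cannot show an acute infusion-related change, and later changes are confounded with recovery in a single-arm study.

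This is a cheap improvement to a component of the primary endpoint. No sample size, error rate or formal inference is affected, because the study tests no hypothesis (Protocol 13.3). A reader might go further and infer that the drug has an undetected haemodynamic effect, or that the sponsor overlooked a known risk. The documents give no evidence of either. The conclusion concerns only what the planned vital-sign tables can and cannot show.

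**What to change.** - **Collection.** In protocol Table 1, 10.1.2.2 and 11.3, and in the SAP 1.2 schedule, add one set of blood pressure, pulse and respiration with the end-of-infusion PK draw and one with the 30 to 60 minute draw, where the subject is still on site.
- **Comparator.** Name the last pre-dose set: the Screening set, or a set repeated at Baseline if Screening falls on an earlier date. This fits the baseline definition in SAP 3.3.8.
- **Analysis.** In SAP 5.3.4 and Table 14.3.6, add the two Day 1 post-dose time points, with change from that comparator, ahead of Day 3. Give each its own nominal time point, because SAP 3.3.6 otherwise keeps only the last of several same-date values. Show the number contributing at each.
- **Cost.** A schedule and CRF amendment, two time points in one table, a few minutes of existing staff time per subject, and extra data entry. The second set will be incomplete for subjects who leave early.
- **If enrolment has closed.** The synopsis estimated last-subject completion in April 2018 and the SAP is dated 14 June 2018, so this may apply. State in the SAP and report that Table 14.3.6 holds no scheduled Day 1 post-dose vital signs and cannot support a conclusion about acute infusion effects.

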### **11.4. Physical Examination**

The Investigator will perform a full physical examination at Screening, including the subject's height and weight, and a targeted physical examination on Day 3 and Day 7 and/or early termination. Examination of the breast and urogenital system may be omitted as per the institution's/investigator's clinical routine. At each follow-up visit, study personnel will evaluate the subject for the presence of clinical signs and/or symptoms of influenza-related complications (see Section 10.2.4). If an IRC is suspected, a targeted physical exam should be conducted to confirm the absence or presence of the IRC.

## **12. PHARMACOKINETIC ASSESSMENTS**

Up to 3 plasma samples will be drawn for determination of peramivir drug concentrations. The samples will be drawn, where possible, during the following time periods, beginning from the end of dosing:

- One time point immediately following completion of the infusion
- One time point from 30 minutes to 1 hour post-infusion
- One time point from 1 hour to 3 hours post-infusion

Plasma samples will be processed and shipped for analysis in accordance with instructions provided in the Laboratory Manual.

Plasma peramivir concentrations will be measured by a validated liquid chromatography-tandem mass spectrometry (LC/MS-MS) assay.

### 13. STATISTICS

Descriptive statistical methods will be used to summarize the data from this study. Unless stated otherwise, the term “descriptive statistics” refers to number of subjects, mean, median, standard deviation (SD), minimum, and maximum for continuous data and frequencies and percentages for categorical data.

All statistical analyses will be conducted with the SAS® System, version 9.1.3 or higher.

#### 13.1. Data Collection Methods

The data will be transcribed from the subjects’ source documents into the Case Report Form (CRF) approved by BioCryst. The data collection methods may be either a paper CRF or an electronic CRF, at BioCryst’s discretion. All documentation supporting the CRF data, such as laboratory or hospital records must be readily available to verify entries in the CRF.

To ensure subject confidentiality, any documents (including laboratory reports, hospital records subsequent to SAEs, etc.) transmitted to BioCryst should not carry the subject’s name.

#### 13.2. Statistical Analysis Plans

A statistical analysis plan (SAP) will be created and approved prior to the review of any data. This document will provide a more technical and detailed description of the proposed data analysis methods and procedures.

#### 13.3. Study Hypothesis

There are no hypotheses to be formally tested in this study.

#### 13.4. Sample Size Estimates

The study is designed to evaluate the safety, PK, and effectiveness of IV administration of peramivir in subjects  $\geq 65$  years of age with influenza infection and in subjects with influenza infection who are at an increased risk of influenza complications. The sample size is not based on statistical considerations, rather a sample size of up to 120 subjects is considered adequate to evaluate the stated objectives.

#### 13.5. Analysis Populations

The populations defined for analysis will include the intent-to-treat (ITT) population, intent-to-treat infected (ITTI) population, safety population, and an exposure-response population. Additional analysis populations may be defined to evaluate study results. Any additional analysis populations will be defined in the SAP.

- **Intent-To-Treat Population:** The ITT population will include all subjects who are randomized. The ITT population will be used for analyses of accountability and demographics.
- **Intent-To-Treat Infected Population:** The ITTI population will include all subjects who are enrolled, treated, and have influenza confirmed by PCR. The ITTI population will be used for analyses of effectiveness.
- **Safety Population:** The safety population will include all subjects who received any amount of study drug. This population will be used for all safety analyses.

- **Exposure-Response Population:** The exposure-response population will include all subjects in the ITTI population who have a quantifiable plasma concentration of peramivir and at least 1 post-baseline effectiveness assessment. This population will be used for all exposure-response analyses.

### 13.6. End of Study Analysis

A final analysis is planned to occur after the last subject completes or discontinues the study, and the resulting clinical database has been cleaned, quality checked, and locked.

### 13.7. General Issues for Statistical Analysis

#### 13.7.1. Multiple Comparisons and Multiplicity

No adjustments are currently planned.

#### 13.7.2. Covariates

Not applicable.

#### 13.7.3. Planned Subgroups

Analyses will be displayed by age group ( $\geq 65$  years vs  $< 65$  years) and viral subtype at Screening. Additional subgroups based on risk of complication may be evaluated. Subgroups will be defined in the SAP.

#### 13.7.4. Missing Data

Every effort will be made to obtain required data at each scheduled visit from all subjects who have been enrolled. In situations where it is not possible to obtain all data, it may be necessary to impute missing data. In assessing the time to event endpoints, subjects who withdraw or never achieve resolution/alleviation, missing data will be censored using the date of subject's last non-missing assessment. Additional details on the handling of missing data will be presented in the SAP.

### 13.8. Effectiveness

#### 13.8.1. Effectiveness Endpoints

All effectiveness endpoints will be summarized using descriptive statistics overall, and by age group and study day/time, if appropriate.

#### 13.8.2. Effectiveness Analyses

Time to resolution of fever, defined as a temperature  $< 99.4^{\circ}\text{F}$  oral with no antipyretic medications taken for at least 12 hours, will be estimated overall and by each age group using the method of Kaplan-Meier. Subjects who do not achieve resolution of fever will be censored at the time of their last assessment.

Time to resolution of influenza symptoms, defined as the time from initiation of study drug until the start of the 21.5-hour period (24 hours- 10%) where all symptoms of influenza are recorded as none or mild, will be estimated overall and for each age group using the method of Kaplan-Meier. Subjects who do not experience alleviation of symptoms will be censored at the time of the last non-missing symptom assessment.

Reduction in viral shedding will be assessed as the change from baseline in  $\log_{10}$  TCID50/mL and RT-PCR, and will be summarized overall, by age group, and by study visit.

Changes in virus susceptibility to neuraminidase inhibitors between virus cultured at Baseline and the last post-treatment sample from which virus can be cultured will be assessed using virology laboratory tests. Virology laboratory tests will include phenotypic characterizations of influenza virus recovered (hemagglutinin and neuraminidase) and viral susceptibility to peramivir, and genotypic analysis of primary virus isolates. These analyses will be presented overall, and separately by age group and viral subtype.

### **13.9. Safety Analyses**

Adverse Events will be mapped to a Medical Dictionary for Regulatory Activities (MedDRA)-preferred term and system organ classification. The occurrence of treatment-emergent AEs (TEAEs) will be summarized by age group and treatment group using MedDRA-preferred terms, system organ classifications, and severity. All AEs will be listed for individual subjects showing both verbatim and preferred terms. Separate summaries of treatment-emergent SAEs and AEs related to study drug will be generated.

Descriptive summaries of vital signs and clinical laboratory results will be presented by age group, treatment group and study visit. Laboratory abnormalities will be graded according to the DAIDS Table for Grading Adverse Events for Adults and Pediatrics (Publish Date: December 2004 Clarification, 2009, see Section 16.2). The number and percentage of subjects experiencing treatment-emergent graded toxicities will be summarized overall and by age group. Laboratory toxicity shifts from baseline to post-baseline assessments will be summarized overall and by age group.

Previous and concomitant medications will be mapped to a WHO preferred term and drug classification. The number and percent of subjects taking concomitant medications will be summarized using preferred terms and drug classifications.

The number and percent of subjects experiencing influenza related complications will be summarized overall and by age group.

Subject disposition will be presented for all subjects. The number of subjects who completed the study and discontinued from the study will be provided. The reasons for early discontinuation also will be presented.

